3.1 Study Objectives

The primary objective of this study is to assess the safety and tolerability of a single short-term and a multiple dose scheme of rhNGF when administered as eye drops in healthy subjects of Japanese ethnicity.

The secondary objective of this study is to assess the pharmacokinetics of single and multiple doses of rhNGF when administered as eye drops in healthy subjects of Japanese ethnicity.

The immunogenicity will be evaluated by determination of the anti-therapeutic antibodies.

3.2 Study Design

This is a Phase I, randomized, double-masked, placebo-controlled eye drops administration study of rhNGF in healthy male and female subjects of Japanese ethnicity.

A total of 30 subjects will be randomized in a masked manner: 20 subjects on rhNGF group and 10 on placebo. A study eye will be assigned to each subject by random. In the study eye, the subjects will be treated with:

- *rhNGF (active) in the rhNGF group.*
- *vehicle (placebo) in the vehicle group.*

Treatment duration is 6 days. The following study treatment will be applied to the study eye:

- *Day 1: One drop study medication (35 µL).*
- *Day 2, 3, 4, 5, 6: One drop of study medication six times a day (every 2h).*

Total dose in the study eye will be 31 drops of study medication over 6 days.

For the fellow eye, vehicle will be administered in parallel to all subjects following the identical schedule as for the study eye.

The study will consist of a screening period of up to 20 days before admission [i.e., Day -21 to Day -1], a one day baseline phase (Day -1) before eye drop application on Days 1 to 6, with follow-up visits on Days 7, 8, 16 ± 2, and 35 (to 42).

3.3 Study Schedule

The protocol visit plan and specification of study procedures and examinations per visit is summarized in Table 1 below.

Table 1: Schedule of Assessments

Visit Day (D)	Drug/ Placebo	AE/ Conmed	PK	Vital Signs	ECG	LAB	ATA	LOT	SLE/CFS TFBUT	IOP	FO	BCDVA	ST	EOE
Screen														
D -21 to -2	Informed Consent, Inclusion/Exclusion Criteria, Demography, Medical History/current medical conditions, Prior medication, Physical Exam, Serology, Drugs Abuse/pregnancy													
				X	X	X			X	X	X*	X	X	X
Baseline														
D -1	Inclusion/Exclusion Criteria, Current Medical Conditions, Adverse Events, Concomitant Medication, Physical Exam, Drugs Abuse/Pregnancy													
		X	X	X	X	X	X	X	X	X	X	X	X	X
Treatment Phase														
Day 1: One drop of either rhNGF or vehicle instilled into study eye (35 µL: 0.70 µg of rhNGF) and one drop of vehicle instilled into the fellow (non-study) eye														
D1	X	X	X	X	X			X	X			X		X
Day 2, 3, 4, 5, 6: One drop of either rhNGF or vehicle six times a day (every 2h) instilled into study eye and one drop of vehicle six times a day (every 2 h) instilled into the fellow (non-study) eye														
D2	X	X	X	X	X			X	X			X		X
D3	X	X	X		X			X	X			X		X
D4	X	X	X		X									
D5	X	X	X		X									
D6	X	X	X	X	X			X	X			X		X
Follow-up														
D7 (FU 1)	Physical Exam													
		X	X		X	X		X	X			X		X
D8 (FU 2)	Physical Exam													
		X	X		X	Y		X	X	X	X	X		X
D16 ± 2 (FU 3)		X	X		X	Y		X	X	X	X	X		X
D35 - 42 (FU 4)		X					X							

ATA – Anti-therapeutic antibodies. BCDVA - Best corrected distance visual acuity (ETDRS). Drugs Abuse/Alcohol breath test/pregnancy. ECG – Electrocardiogram. EOE - External ocular examination (motility and eyelids). FO –Fundus Ophthalmoscopic examination (*dilated FO only at Screening). IOP – Intraocular Pressure. LAB - Laboratory Safety Tests - Hematology, Biochemistry, Urinalysis. ATA – Anti-therapeutic antibodies. LOT - Local Ocular Tolerability - Visual Analogue Scale (VAS). LOT always to be applied before the SLE FO and/or IOP (if applicable). Physical exam. PK – Pharmacokinetics. Serology: Hepatitis/HIV and for postmenopausal females FSH Laboratory Safety Tests. SLE/CFS/TFBUT - Slit lamp examination (SLE): eyelid margin, conjunctiva, cornea, anterior chamber, iris and lens with the instillation of fluorescein to evaluate corneal fluorescein staining and tear film break-up time (TFBUT). ST - Schirmer's test (ST) without anesthesia. Vital Signs - blood pressure, pulse rate, respiratory rate and oral body temperature. A detailed view of the evaluations is provided in protocol Appendix 3 – Detailed List of Procedures

3.4 Primary and Secondary Study Endpoints

Primary safety endpoints are:

- *Incidence of treatment emergent adverse events (TEAEs).
TEAEs are defined as an adverse event (AE), which start after first dose of study treatment. These comprise AEs during the treatment and follow-up period.*
- *Incidence of treatment emergent adverse events during 1st dose schedule (TEAEs Dose 1).
TEAEs Dose 1 are defined as TEAEs, which start after first dose of study treatment and before administration of the first dose at Treatment Day 2.*
- *Incidence of treatment emergent adverse events during 2nd dose schedule (TEAEs Dose 2).
TEAEs Dose 2 are defined as TEAEs, which start on/after the first dose at Treatment Day 2 and before Follow Up Day 7 (FU1) visit.*

Secondary safety endpoints are:

- *Incidence of Follow-Up AEs (FUAE)
FUAEs are defined as TEAEs which start on or after Follow Up Day 7 (FU1) visit visit.*
- *Incidence of ocular TEAEs by eyes.*
- *Course of ECG parameters ventricular rate, PR interval, QRS duration and QT interval over all visits.*
- *Course of vital signs parameters systolic and diastolic blood pressure, pulse rate, respiratory rate and oral body temperature over all visits.*
- *Changes from baseline in biochemistry parameters over all visits.
Baseline is defined as the Laboratory assessment of Baseline (D-1) Visit*
- *Changes from baseline in haematology parameters over all visits.
Baseline is defined as the Laboratory assessment of Baseline (D-1) Visit*
- *Shift in overall interpretation of urinalysis over all visits. Laboratory assessment at Baseline (D-1) Visit is considered as reference for assessing the shift.*
- *Course of intraocular pressure by eye over all visits.*
- *Course of visual acuity score by eyes over all visits
The visual acuity score will be derived as the total numbers of letters, which were read correctly at 4 meter plus the total number of letters read at 1 meter as collected on the eCRF page. When 20 or more letters are read at 4 meters the visual acuity score for that eye is recorded as the number of letters correct at 4 meters plus 30. The subject gets credit for the 30 letters at 1 meter even though they did not have to read them. If no letters are read correctly at either 4.0 meters or 1 meter, then the visual acuity score is recorded as "0."*

- *Course of LogMAR by eyes over all visits.
The logMAR will be derived as $-\log$ (Snellen Equivalent result)*
- *Course of TFBUT by eye over all visits.*
- *Course of overall NEI score by eye over all visits.*

Primary tolerability endpoints are:

- *Change from baseline in VAS ocular tolerability scores at Treatment Day 2 pre-dose in study eye (Tolerability of $1 \times 0.70 \mu\text{g}$ rh-NGF per day).
Baseline is defined as the pre-treatment assessment at the Baseline (D-1) visit.*
- *Change from baseline in VAS ocular tolerability scores at D2 8h, D3 pre-dose, D6 pre-dose, D6 8h, D7 (Follow-up Day 7), D8 (Follow-up Day 8), D16 (Follow-up Day 16) in study eye (Tolerability of $6 \times 0.70 \mu\text{g}$ rh-NGF per day).
Baseline is defined as the pre-treatment assessment at the Treatment Day 2 visit.*

Secondary tolerability endpoints are:

- *Course of VAS ocular tolerability scores by eye over all visits.*
- *Intraindividual change in VAS ocular tolerability scores between study eye and fellow (non-study) eye at all study visits.*

Pharmacokinetics endpoints

The kinetics of single dose administration as well as multiple dose assessment will be evaluated. Two validated ELISA tests will be used for PK measurements.

Beyond the respective rhNGF plasma levels for both ELISA methods, the following parameters will only be investigated for each ELISA method, if the data warrant to do so:

- *maximum observed serum concentration (C_{max}), time to reach C_{max} (t_{max}), time elapsed between dosing and the first serum concentration that exceeds the assay quantification limit (t_{lag}) as measured without treatment based on assessments on D-1*
- *C_{max} , t_{max} , t_{lag} of single dose regimen based on assessments on D1 and pre-dose of D2*
- *C_{max} , t_{max} , t_{lag} of multiple dose regimen based on assessments atating with pre-dose of D2*
- *serum concentration measured before the administration of the next dose (C_{trough}) as assessed at pre-dose visit on D2, D3, D4, D5, D6*
- *$AUC_{[0-24]}$ for the single dose regimen and the first day of multiple dose regimen. $AUC_{[0-24]}$ as area under the serum concentration versus time curve from time 0 h to pre-dose value of the next day calculated by the linear trapezoidal rule. Values below the level of quantitation will be set to 0. Values below the baseline concentration will be set to zero other than for the values for which no later values above the baseline concentration are available, which will be set to missing.*
- *$AUC_{0-t_{last}}$ for the multiple dose regimen. This is derived as area under the serum concentration versus time curve from time 0 h to the last data point t_{last} after drug*

administration above the limit of quantitation and the baseline concentration, calculated by the linear trapezoidal rule.

Values below the baseline concentration will be set to zero other than for the values for which no later values above the baseline concentration are available, which will be set to missing

- *AUC for the multiple dose regimen. AUC will be derived as area under the serum concentration versus time curve extrapolated to infinity, calculated as $AUC = AUC_{0-last} + C_{last}/\lambda_z$*

Immunogenicity

Anti-Therapeutic Antibodies (ATA) serum levels will be evaluated for immunogenicity. *The serum concentrations of ATA will be provided by the bioanalytical laboratory in a separate report and incorporated into the final CSR as an appendix.*

A more detailed description on all study endpoints on derivation of study endpoints is provided in section 7.2 of the SAP.

3.5 Interim Analyses

No interim analysis is planned.

3.6 Changes in the Conduct of Study or Planned Analysis compared to Protocol

The following changes of the study conduct did affect the planned analysis:

- Study protocol section 8.2 describes the assessment of “daily consumption of caffeine”. This was not collected on the eCRF and is therefore not presented in the analysis.
- Study protocol section 8.2 describes the assessment of “daily consumption of alcohol”. However, assessment of usual alcohol consumption was changed to weekly assessment to facilitate verification of exclusion criterion 7.
- Study protocol section 7 describes the assessment of body weight for all scheduled assessment times of vital sign. However, body weight was assessed on the eCRF only at Screening Visit. As a consequence, no presentation of post-baseline body weight will be provided.
- No clinical interpretation are recorded for urinalysis including the endpoint “overall interpretation of urinalysis results”. As a consequence, this endpoint will not be analyzed.
- In the study protocol section 8.2, assessment of the horizontal diameter of the cornea is specified as part of the slit lamp evaluation. However, this was not collected in the eCRF and is therefore not part of the analysis.
- For Fundus Ophthalmology, the site did perform additional unscheduled assessments in a non-dilated manner at D1 8hr and D2 pre-dose. These assessments were done without any specific safety reason, so results were not entered in the eCRF as unscheduled assessments and are therefore not included in the data listings.

The following refinements of the pre-planned analysis in the study protocol were implemented in this SAP:

- For a better perceivability, the primary safety endpoints are rephrased to Incidence of Treatment Emergent Adverse Events during Single/Multiple Dose Scheme, respectively.
- In the eCRF, no start time of Adverse Event has been recorded. During SAP creation, this was considered as required for a precise assignment of AEs to Single-Dose or Multiple Dose Scheme. and multiple dose treatment phase. As a consequence, the start times of an AE was entered in the eCRF as free-text comment associated to the AE start date field.
- Fundus Ophthalmology was performed in a dilated manner at Screening Visit, whereas a non-dilated Fundus Ophthalmological assessment was done for all other study visits. As a consequence, data listings will clearly indicate the mode of fundus ophthalmological assessments.
- Study protocol section 8.6 describes the ECG assessments heart rate, PR interval, QRS duration, QT interval as well as QTc (Fridericia and Bazett corrections), whereas in section 10.1 ventricular rate, PR interval, QRS duration and QT interval were specified as secondary ECG endpoints. For the secondary endpoint analysis, all recorderd parameters mentioned in section 8.6 were considered as secondary safety endpoints.
- For Corneal Staining, the study protocol states in headers that a modified Oxford Scale is to be assessed. However, the details of assessment in section 8.12 and the study endpoints as described in protocol section 10.1 describes the NEI grading for corneal and conjunctival staining, which has been applied to the site and were analyzed accordingly. To accommodate for regulatory purposes, a post-hoc assessment of modified Oxford Scale (MOS) is performed by the investigator based on documented NEI source data before the BDRM.

The MOS assessments will be used for a verification of Exclusion Criterion 18 *“Presence of any corneal opacity or corneal fluorescein staining > 0.5 grade using the modified Oxford Scale in either eye at screening or baseline”* during the BDRM.

For the analysis, NEI scales will be analysed as planned in the study protocol. The collected MOS values will be mapped into SDTM version only.

4 General Definitions

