8.7 Laboratory Safety Tests

The following laboratory evaluations will be performed at the study site:

The subject need not be in fasting condition. Examinations marked with Y instead of X in Appendix 3-Detailed List And Timing Of Procedures (§ 15.3) may be done at any time on the examination day.

Hematology: hemoglobin, hematocrit, RBC count, reticulocyte count, WBC with differential platelet count.

Clinical Chemistry: sodium, potassium, chloride, calcium, inorganic phosphorus, total protein, albumin, total bilirubin, AST, ALT, alkaline phosphatase, GGT, FSH (only for postmenopausal females at Screening to confirm post-menopausal status), creatinine, BUN(urea-N), glucose, uric acid, cholesterol and high sensitivity C-reactive protein.

Urinalysis Stix: pH, density, glucose, protein, blood (free Hb), bilirubin, urobilinogen, ketones, nitrites, leukocytes and erythrocytes. A midstream urine sample (approx. 30 mL) will be obtained, in order to avoid contamination and allow a proper assessment.

Pregnancy test (females only): Performed in serum at Screening and in Urine during the Baseline period

For all laboratory values, date and time of laboratory sample will be documented on the eCRF. Laboratory results will be categorized either Normal, abnormal not clinically significant, abnormal clinical significant by the investigator. Each laboratory value determined in the study as well as the clinical assessments will be entered on the eCRF.

Clinically significant changes (or a clinically significant worsening) in laboratory safety assessments, which were observed the first time during study will be reported as adverse events.

Values which are considered clinically significant and/ or study drug related will be noted on the eCRF. The investigator will record his/ her medical opinion of the clinical significance of each laboratory value outside of the reference range in the eCRF. This decision shall be based upon the nature and degree of the observed abnormality. The investigator may choose to repeat any abnormal result ONCE, in order to rule out laboratory error. Clinically relevant deviations of laboratory test results occurring during or at post study examination of the study must be reported and discussed with the sponsor's Medical Expert. Repeated evaluations are mandatory until their normalization or until the time course and reason of the underlying process can clearly be assessed. In case of doubt, the sponsor's Medical Expert must be contacted.

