10 STATISTICS

10.1 Study endpoints

Primary safety endpoints are:

- Incidence of treatment emergent adverse events (TEAEs).
TEAEs are defined as an adverse event (AE), which start after first dose of study treatment. These comprise AEs during the treatment and follow-up period.
- Incidence of treatment emergent adverse events during 1st dose schedule (TEAEs Dose 1).
TEAEs Dose 1 are defined as TEAEs, which start after first dose of study treatment and before administration of the first dose at Treatment Day 2.
- Incidence of treatment emergent adverse events during 2nd dose schedule (TEAEs Dose 2).
TEAEs Dose 2 are defined as TEAEs, which start on/after the first dose at Treatment Day 2 and before Follow Up Day 7 (FU1) visit.

Secondary safety endpoints are:

- Incidence of Follow-Up AEs (FUAE)
FUAEs are defined as TEAEs which start on or after Follow Up Day 7 (FU1) visit visit.
- Incidence of ocular TEAEs by eyes.
- Course of ECG parameters ventricular rate, PR interval, QRS duration and QT interval over all visits.
- Course of vital signs parameters systolic and diastolic blood pressure, pulse rate, respiratory rate and body temperature over all visits.
- Changes from baseline in biochemistry parameters over all visits.
Baseline is defined as the Laboratory assessment of Baseline (D-1) Visit
- Changes from baseline in hematology parameters over all visits.
Baseline is defined as the Laboratory assessment of Baseline (D-1) Visit
- Shift in overall interpretation of urinalysis over all visits. Laboratory assessment at Baseline (D-1) Visit is considered as reference for assessing the shift.
- Course of intraocular pressure by eye over all visits.
- Course of visual acuity score by eyes over all visits
The visual acuity score will be derived as the total numbers of letters, which were read correctly at 4 meter plus the total number of letters read at 1 meter as collected on the eCRF page. When 20 or more letters are read at 4 meters the visual acuity score for that eye is recorded as the number of letters correct at 4 meters plus 30. The subject gets credit for the 30 letters at 1 meter even though they did not have to read them. If no letters are read correctly at either 4.0 meters or 1 meter, then the visual acuity score is recorded as "0."
- Course of LogMAR by eyes over all visits.
The logMAR will be derived as – log (Snellen Equivalent result)
- Course of TFBUT by eye over all visits.

- Course of overall NEI score by eye over all visits.

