7.2.11 Secondary Safety Endpoints – Laboratory Safety Data

The following laboratory evaluations will be performed at the study site:

Haematology: hemoglobin, hematocrit, RBC count, reticulocyte count, WBC with differential platelet count.

Biochemistry: sodium, potassium, chloride, calcium, inorganic phosphorus, total protein, albumin, total bilirubin, AST, ALT, alkaline phosphatase, GGT, FSH (only for postmenopausal females at Screening to confirm post-menopausal status), creatinine, BUN(urea-N), glucose, uric acid, cholesterol and high sensitivity C-reactive protein.

Urinalysis Stix: pH, density, glucose, protein, blood (free Hb), bilirubin, urobilinogen, ketones, nitrites, leukocytes and erythrocytes. A midstream urine sample (approx. 30 mL) will be obtained, in order to avoid contamination and allow a proper assessment.

The subject need not be in fasting condition.

Laboratory results will be categorized either as normal, abnormal not clinically significant, abnormal clinical significant by the investigator. Each laboratory value determined in the study as well as the clinical assessments will be entered on the eCRF.

Clinically significant changes (or a clinically significant worsening) in laboratory safety assessments, which were observed the first time during study will be reported as adverse events.

The investigator may choose to repeat any abnormal result ONCE, in order to rule out laboratory error. Repeated evaluations are mandatory until their normalization or until the time course and reason of the underlying process can clearly be assessed.

Laboratory Safety Assessments are performed at Screening Visit, Baseline Visit, FU1, FU2, FU3 and are documented on eCRF Pages “Haematology”, “Chemistry” and “Urinalysis”, respectively. These assessment may be done at any time on the scheduled examination day.

For the presentation of data, the clinical evaluation as documented on the eCRF page will be utilized, i.e. no derivation of Normal/Abnormal values will be done for analysis purposes. As a consequence, a missing clinical evaluation will be presented as missing.

For this single center study, the laboratory parameters will be presented in the units, in which they were collected, i.e. no transformation into SI units will be performed.

For the secondary evaluations, all observed hematology and biochemistry parameters (except FSH-test) will be described as well as corresponding Changes from Baseline (D-1).

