The documented results for FSH and urinalysis will be listed.

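### The secondary urinalysis shift endpoint is dropped for want of a recorded interpretation, though masked grading of the collected dipstick results before unmasking could supply a close substitute

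*SAP*

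**What the plan says.** Protocol 10.1 (Study endpoints) lists among the secondary safety endpoints: "Shift in overall interpretation of urinalysis over all visits". SAP 3.4 carries it over with the same reference visit: "Laboratory assessment at Baseline (D-1) Visit is considered as reference for assessing the shift".

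Protocol 8.7 says how the interpretation was to arise: "Laboratory results will be categorized either Normal, abnormal not clinically significant, abnormal clinical significant by the investigator". It also requires that it be captured: "Each laboratory value determined in the study as well as the clinical assessments will be entered on the eCRF".

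SAP 3.6 reports that this did not happen for urinalysis: "No clinical interpretation are recorded for urinalysis including the endpoint" (the sentence goes on to name the overall interpretation). It concludes: "As a consequence, this endpoint will not be analyzed".

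SAP 7.2.11 places laboratory assessments, including a Urinalysis eCRF page, at Screening, Baseline, FU1, FU2 and FU3. On reporting it says: "The documented results for FSH and urinalysis will be listed". For laboratory data generally it says: "For the presentation of data, the clinical evaluation as documented on the eCRF page will be utilized", and it rules out deriving normal or abnormal status for the analysis. SAP 10.7.3 plans summaries for haematology and chemistry only. The list in SAP 12 holds Listing 16.2.08-4.3 for urinalysis and no urinalysis table.

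**The concern.** A safety endpoint named in the protocol is left unanswered, although the measurements behind it were scheduled and have their own eCRF page. What is missing is the investigator's reading of those measurements. That reading can still be made from the recorded results while the treatment code is closed, or replaced by a simpler rule that is declared as such.

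Safety and tolerability are the primary objective. Without a table by arm, a reader of the study report must go through a subject listing to learn whether urinalysis findings moved from normal to abnormal more often on rhNGF than on vehicle. The SAP also disagrees with itself: 3.4 lists the endpoint, 8.1 says all endpoints are summarised, 7.2.11 says that laboratory results are categorised by the investigator, and 3.6 says that for urinalysis they were not.

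**Working it through.** The plan gives no figure to reproduce on this point. There is no formal sample size (Protocol 10.2) and no inference (SAP 8.2). The check is a comparison of sections plus a simple count.

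**1. Is the endpoint dropped?** Yes. It is named in Protocol 10.1 and SAP 3.4 and withdrawn in SAP 3.6. Planned urinalysis tables: 0. Planned urinalysis listings: 1.

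**2. Were the underlying data to be collected?** Yes. SAP 7.2.11 names 11 dipstick parameters: pH, density, glucose, protein, blood, bilirubin, urobilinogen, ketones, nitrites, leukocytes and erythrocytes. The schedule has one Day -1 assessment and three follow-ups (FU1, FU2, FU3).

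**3. Is there a basis for calling a result normal or abnormal?** Protocol 8.7 places the urinalysis at the study site and requires a tabulation of normal ranges for the sponsor. Protocol 12.4 requires the normal ranges of all laboratory tests performed at the site before initiation. Neither section says that these ranges are held in the eCRF.

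**4. Is there time to repair the gap without bias?** SAP 8.3.3 puts the blind data review meeting before database lock and code break. SAP 3.6 records two comparable repairs: adverse event start times were added as free-text comments, and the modified Oxford scale was graded afterwards by the investigator from source data before that meeting.

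**5. How much is involved?** Inputs are 30 subjects, 20 on rhNGF and 10 on vehicle (Protocol 3.3), and 3 post-baseline visits. The endpoint is one overall interpretation per subject and visit.

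- All subjects: 30 x 3 = 90 baseline-to-follow-up pairs
- rhNGF: 20 x 3 = 60
- Vehicle: 10 x 3 = 30
- Overall gradings needed if done by the investigator: 30 x (1 + 3) = 120

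These are upper limits that assume every subject attends every visit.

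**6. Would a mechanical overall rule do?** Not well. Suppose a sample is called abnormal when any of the 11 parameters is out of range. Take as an assumption that each parameter is out of range by chance with probability 1% to 5%, independently. The share of normal samples flagged is then 1 - 0.99^11 = 0.10 to 1 - 0.95^11 = 0.43. Such a rule has no step for clinical significance, so it is not the protocol's endpoint.

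**The case against.** The strongest reply is that an overall interpretation is an investigator's judgement in three categories, and no program can recover it from dipstick values. That stands. Any substitute must either be a judgement, made masked, or be labelled as something different.

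The change is also disclosed, with its cause, in the section meant for that purpose, and SAP 3.4 reproduces protocol text by the convention stated in SAP 3. Nothing is hidden, and the leftover wording is untidy rather than misleading. It still needs aligning.

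Clinically significant laboratory changes are to be reported as adverse events, and these are tabulated by arm. This helps only in part. The route depends on a judgement of clinical significance, and SAP 3.6 says that no such interpretation was recorded for urinalysis, so the data cannot show that it was made.

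A listing of 30 subjects does show individual changes, and Protocol 2.6 reports no treatment effect on urinalyses in the earlier healthy-volunteer study at up to 180 µg/mL, which is 180/20 = 9 times this concentration. Both points lower the stakes. Neither reports the endpoint.

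A reader might go further and ask for shift tables for haematology and chemistry, because SAP 7.2.11 says the recorded evaluation will be used. The protocol endpoints there are changes from baseline, which the SAP delivers. The recorded evaluation can appear in the listings, and the mock shells are in a separate document. Such tables are a preference, not a gap in the plan.

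**Conclusion.** The point holds as a minor one that should be corrected. A protocol-named secondary safety endpoint is withdrawn for a reason that does not compel its withdrawal, and up to 90 subject-visit pairs (60 rhNGF, 30 vehicle) get no summary by arm. No primary endpoint, inference or power statement is affected.

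This rests on three assumptions: the dipstick results were entered as scheduled, the site's ranges cover the dipstick parameters, and the treatment code is still closed when the repair is made.

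Three stronger readings are not supported:

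- A reader might infer that every dipstick result is in the database. The SAP names the eCRF page and the visits but does not confirm completeness.
- A reader might count 11 x 3 x 30 = 990 unreported results. That counts parameter-level values, which the protocol does not name as endpoints; the endpoint is one overall interpretation per subject and visit.
- A reader might treat this as the first study in this population and raise the stakes accordingly. The documents say only that the results will allow development in subjects of Japanese ethnicity.

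**What to change.** In SAP 3.6 and 7.2.11, replace the statement that the endpoint is not analysed by one of two options:

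- **(a) Masked grading.** Before the blind data review meeting, the investigator gives each sample an overall grade (normal, abnormal not clinically significant, abnormal clinically significant) from the recorded dipstick values, without the treatment code, as was done for the modified Oxford scale. This is closer to the protocol endpoint.
- **(b) Derived substitute.** For each parameter, define normal or abnormal against the site's reference range, with the rules fixed before unmasking, and label the result as a derived substitute. SAP 7.2.11 then needs an exception to its rule against deriving normal/abnormal status.

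Under either option, add one table by arm for the Safety Set showing the shift from Day -1 to FU1, FU2 and FU3, and add it to SAP 10.7.3 and 12. Align SAP 3.4 and 7.2.11 with what will be reported; SAP 8.1 can then stand as written.

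The cost is up to 120 gradings under (a), or a short set of range rules under (b), plus one table. The limitation to state in the report is that neither option is the contemporaneous investigator interpretation that the protocol intended.
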